# 3. LIST OF ABBREVIATIONS AND DEFINITIONS OF TERMS

	Definition
AE	Adverse event
AUC	Area under the concentration-time curve
BUN	Blood urea nitrogen
$C_{max}$	Peak plasma concentration
$C_{\min}$	Trough plasma concentration
C-CASA	Columbia Classification Algorithm of Suicide Assessment
CNS	Central nervous system
CRO	Contract research organization
C-SSRS	Columbia-Suicide Severity Rating Scale
ECG	Electrocardiogram
eCRF	Electronic case report form
GABA	Gamma-aminobutyric acid
GCP	Good Clinical Practice
ICH	International Conference on Harmonisation of Technical
	Requirements for Registration of Pharmaceuticals for
	Human Use
IEC	Independent Ethics Committee
IND	Investigational New Drug application
IRB	Institutional Review Board
MedDRA	Medical dictionary for regulatory activities
mg	Milligram(s)
mL	Milliliter(s)
mm	Millimeter
MS	Multiple sclerosis
ng	Nanogram(s)
PI	Principal Investigator
QC	Quality control
RBC	Red blood cell
SAE	Serious adverse event
SOP	Standard operating procedures
SPARC	Sun Pharma Advanced Research Company
$T_{max}$	Time to peak concentration
WBC	White blood cell

Confidential Page 11 of 47

# 5. INTRODUCTION

This protocol describes a clinical study designed to investigate the long term safety of when administered in subjects with spasticity due to multiple sclerosis (MS).

This clinical trial will be conducted in compliance with Good Clinical Practices (GCP) including the Declaration of Helsinki and all applicable regulatory requirements.

# 5.1. Background

MS is the most common neurological disease of young adults. MS is characterized by the appearance of scattered plaques of demyelinated axons in the central nervous system (CNS). The Multiple Sclerosis Association of America estimates that there are approximately 400,000 individuals in the United States diagnosed with MS and about 10,000 new cases per year. As reviewed by Paisley et al, spasticity is a major contributor to disability in MS.¹ It is estimated that between 40 and 75% of all subjects are affected. The survey by the MS Society¹ reported fatigue, spasticity (stiffness, spasms, or both), and problems with balance as the most commonly experienced symptoms. Overall, 64% of respondents reported muscle stiffness, 51% muscle spasms, and 74% reported stiffness, spasms, or both. Spasticity consists of an abnormal, velocity-dependent increase in the phasic and muscle tonic stretch reflexes, due to an abnormal integration of the nervous system motor responses to sensory input.

Confidential Page 15 of 47

[figure not shown]

# 5.2.1. Nonclinical Studies

[figure not shown]
A comprehensive battery of nonclinical studies has been performed with

. Please refer to the Investigator's Brochure for a complete summary of nonclinical data for

[figure not shown]
Confidential Page 16 of 47

[figure not shown]
Confidential Page 17 of 47

Confidential Page 18 of 47

### 5.3. Trial Rationale

## 6. TRIAL OBJECTIVE AND PURPOSE

The objective of this study is to investigate the long term safety of when administered to subjects aged 18 years and older.

Confidential Page 19 of 47

# 7. TRIAL DESIGN

# 7.1. Type and Design of Trial

This is a multicenter, open-label, safety study in subjects with spasticity due to MS. Approximately 550 potential subjects will be screened to yield 350 subjects enrolled in approximately 35-40 centers, in order to obtain safety data from at least 250 subjects who have completed at least 26 weeks of treatment and at least 100 subjects will have completed at least 1 year of treatment.

Subjects enrolled in clinical trial CLR\_09\_21 who completed the double-blind randomized withdrawal phase (Part 3) of that trial will be eligible to participate in this trial.

Informed consent will be obtained from subjects prior to the initiation of any trial-specific procedures.

Visits are scheduled on: Days -14 (Week -2), 1 (Week 1), 28 (Week 4), 84 (Week 12), 182 (Week 26), and during 3 month interval, follow-up visits.

# 7.2. Trial Endpoints

The trial endpoints to be evaluated are safety parameters including vital signs, clinical laboratory results, 12-lead electrocardiogram (ECG), physical examination and neurological examination results, and treatment emergent adverse events (AEs).

# 7.3. Subject Number

Subjects enrolling CLR\_11\_04 will retain the same subject number as was assigned to them in the CLR\_09\_21 trial.

The subject number will uniquely identify each enrolled subject. The subject number will appear on all study documents relating to that subject and will be cross-referenced by the subject's initials and age.

#### 8. SUBJECT POPULATION

# 8.1. Number of Subjects

Approximately 550 potential subjects will be screened to yield 350 subjects enrolled in approximately 35-40 centers, in order to obtain safety data from at least 250 subjects who have completed at least 26 weeks of treatment and at least 100 subjects will have completed at least 1 year of treatment.

Confidential Page 20 of 47

## 8.2. Inclusion Criteria

Subjects are required to give written consent to participate in the trial. They will be informed that their primary medical practitioner and physiotherapist may be contacted to inform them of the trial and its conditions. Subjects must meet all entry criteria listed below.

- 1. Willingness to participate and give written informed consent
- Men and women ≥ 18 years of age
- 3. Sexually active women who are of child bearing potential will practice an acceptable method of birth control for the duration of the trial as judged by the investigator. Examples of acceptable contraception are: condoms, foams, jellies, diaphragm, intrauterine device, oral or long acting injected contraceptives, bilateral tubal ligation, bilateral oophorectomy, hysterectomy, or having a partner who is incapable of initiating conception. The practice of contraception must have started at least 3 months prior to trial entry.
- 4. If female, negative pregnancy test result at Screening
- 5. Diagnosed with MS and a known history of spasticity
- 6. Completed the double-blind randomized withdrawal phase (Part 3) of trial CLR\_09\_21 with no major protocol violation

#### 8.3. Exclusion Criteria

Subjects will be excluded from the trial if any of the following exclusion criteria apply prior to enrollment:

- 2. History of alcohol abuse or use of recreational drugs within 12 months prior to Visit 1
- 3. History of chronic use of concomitant medications in neurologic or psychiatric illness which would affect the assessment of the safety of the trial medication
- 4. If the investigator feels that participation in this study is not in the best interest of the subject.

#### 8.4. Withdrawal Criteria

The subject will receive oral and written information about the trial, which includes information about the right to withdraw from the trial at any time without prejudice to future treatment. In this case, the subject must immediately contact the investigator and inform the investigator that he/she is leaving the trial. The subject will be encouraged to provide the reason for wishing to withdraw. The subject must return the trial drug as well as undergo early study termination procedures.

The investigator must withdraw a subject from the trial in the following cases:

Occurrence of an AE which does not justify a continuation of the trial in that subject

Confidential Page 21 of 47

Major protocol violation which jeopardizes the interpretation of that subject's data

The following are additional justifiable reasons for removing a subject from the trial:

- Subject experiences intolerable spasticity
- Subject has a treatment related SAE
- Subject becomes pregnant during the trial
- If, in the investigator's opinion, continuation in the trial would be detrimental to the subject's well being

## 9. TREATMENT OF SUBJECTS

## 9.1. Trial Medications

The study drug, is manufactured by SPARC Ltd., India.

The batch numbers including the certificate of analysis and stability documentation will be maintained in the trial master file.

# 9.2. Treatment Doses

[figure not shown]
Subjects are to maintain a Subject Diary (Appendix 1) to record missed doses and other events or issues. The clinic will review the diaries with the subjects during the subsequent visits.

## 9.2.1. Trial CLR 09 21

Study CLR\_11\_04 will open for enrollment while study CLR\_09\_21 is ongoing. Blinded study medication will be temporarily dispensed to all subjects enrolled into CLR 11 04 who have exited study CLR 09 21 for the first 4 weeks of the study.

Blinded study medication for subjects in the first month of study CLR\_11\_04 will

Confidential Page 22 of 47

## 9.3. Concomitant Medications

All concomitant treatments must be appropriately recorded and described in the electronic case report form (eCRF).

# 9.4. Study Drug Administration

Subjects will be instructed to take study medication at the same time of day

# 9.5. Treatment Compliance

Treatment compliance will be measured on the basis of a capsule count by the investigator or his/her designee every time drug supplies are returned. Each subject will be instructed to bring the study medication (with the capsules that remain) with him/her to the next scheduled visit. If the subject fails to bring the study medication on the designated day, he/she will be told to bring the study medication within the next 3 days. If the subject fails to do so, the capsule count will be recorded as "not available."

## **Subject Diary (Appendix 1):**

Confidential Page 23 of 47

A Subject Diary will be utilized to assess compliance and collect comments regarding any important problems or issues (missed dose, reason for missing dose, disturbing signs/symptoms, etc) associated with this trial. The clinic staff will review the diary during each visit. Comments that may suggest AEs will be reviewed with the subject to determine the actual presence of AEs. Any missed doses will be recorded in the diary, along with the reason for the missed dose. The diary will help confirm the level of drug compliance in this study.

# 9.6. Withdrawal From the Study

#### 9.6.1. Premature Discontinuation of Subject in the Trial

The investigator will make every effort to keep each subject in the study. However, should a subject be removed from the study or elect to decline further study participation, the information will be recorded on the appropriate page in the eCRF, and the primary reason for discontinuation will be selected: 1) adverse event; 2) major protocol violation; 3) lost to follow-up; 4) worsening of clinical condition or loss of efficacy; or 5) other (for which the reason should be clearly stated).

As far as possible, all assessments and procedures scheduled for the end-of-trial visit must be performed on all subjects who receive trial medication but do not complete the trial according to protocol. The subject must return all unused investigational products.

Subjects who are withdrawn from the trial due to AEs will be treated according to established acceptable medical practice and will be followed for outcome. All pertinent information concerning the outcome of such treatment will be entered in the eCRF.

The investigator will make every effort to contact subjects lost to follow-up.

#### 9.6.2. Discontinuation of the Trial

SPARC Ltd. may discontinue the trial at any time, for ethical, scientific, or business reasons. The investigator is entitled at any time to stop his or her participation in the trial due to medical reasons. In such a case, he/she should consult SPARC Ltd. at the earliest opportunity.

If the study is prematurely terminated or suspended, the Institutional Review Board/Independent Ethics Committee (IRB/IEC) and the regulatory authorities will be informed promptly and will be provided with the reasons for the termination or suspension by the investigator and SPARC Ltd., respectively.

# 10. SEQUENCE OF PROCEDURES

Table 1 summarizes all visits and study procedures by time point.

Visits will be scheduled on: Days -14 (Week -2), 1 (Week 1), 28 (Week 4), 84 (Week 12), 182 (Week 26), and at 3 month interval visits.

Confidential Page 24 of 47

# 10.1. General Conduct of the Trial

[figure not shown]
Written informed consent will be obtained for this trial by the Principal Investigator (PI) or his/her designee from all subjects before the performance of any protocol-specific procedure.

# 10.2. Screening (Visit 1, Day -14 to Day -1/Week -2)

All potential subjects who have not completed CLR\_09\_21 will complete all CLR\_11\_04 assessments during the Screening Visit.

- Written informed consent will be obtained
- Medical history and demographic information will be obtained
- A physical examination will be performed
- A neurological examination will be performed
- A urine pregnancy test will be performed (if applicable)
- Vital Signs (sitting), after resting for 5 minutes, will be obtained
- Clinical laboratory testing will be performed including hematology (red blood cell [RBC] count, hemoglobin, total and differential white blood cell [WBC] count, platelet count), and serum chemistry including sodium, potassium, chloride, blood urea nitrogen [BUN], and creatinine
- A 12-lead ECG will be performed in triplicate

- Concomitant medication and physical therapy will be recorded
- Study medication and diary will be dispensed. Study medication will be dispensed via IVRS/IWRS
- The next trial visit will be scheduled

# 10.3. Baseline (Visit 2, Day 1/Week 1)

During this visit, the investigator will review all entry criteria, making certain that the potential subject meets all criteria. In addition, the following procedures will be performed:

- AEs will be recorded for all subjects Concomitant medications will be recorded
- Study medication and Subject diary collected and reviewed from previous visit for compliance
- Study medication and diary will be dispensed via IVRS/IWRS
- The next trial visit will be scheduled

Confidential Page 25 of 47

# 10.4. Visits 3 (Day $28 \pm 5$ days/Week 4) and 4 (Day $84 \pm 5$ days/Week 12)

- Vital Signs (sitting), after resting for 5 minutes, will be obtained
- A 12-lead ECG will be performed in triplicate
- Concomitant medication and physical therapy will be recorded
- AEs will be recorded
- A urine pregnancy test will be performed
- Study medication and Subject diary collected and reviewed from previous visit for compliance
- Study medication and subject diary will be dispensed
- The next trial visit will be scheduled

# 10.5. Visit 5 (Day 182 $\pm$ 5 days/Week 26), or Premature Termination

- Physical and neurologic examinations will be performed during Visit 5, but will be performed as needed during the Premature Termination visit to follow the resolution of any adverse events
- A urine pregnancy test will be performed
- Vital Signs (sitting), after resting for 5 minutes, will be obtained
- Clinical laboratory testing will be performed including hematology (RBC count, hemoglobin, total and differential WBC count, platelet count), and serum chemistry including sodium, potassium, chloride, BUN, and creatinine
- A 12-lead ECG will be performed in triplicate. 12-lead ECG should be performed at the Premature Termination visit, as needed, in order to follow adverse events to resolution.
- C-SSRS assessment will be performed
- Concomitant medication and physical therapy will be recorded
- AEs will be recorded
- Study medication and Subject diary collected and reviewed from previous visit for compliance
- Study medication and subject diary will be dispensed
- The next trial visit will be scheduled.

# 10.6. Visits Every 3 Months after Visit 5 (90 $\pm$ 5 days following Visit 5 and all subsequent visits)

- Concomitant medication and physical therapy will be recorded
- AEs will be recorded
- A urine pregnancy test will be performed
- C-SSRS assessment will be performed
- Study medication and Subject diary will be dispensed (for subjects continuing on treatment only)

Confidential Page 26 of 47

- Study medication and Subject diary collected and reviewed from previous visit for compliance
- The next trial visit will be scheduled

## 10.7. Unscheduled Visits

- Concomitant medication and physical therapy will be recorded
- AEs will be recorded
- Study drug dose may be adjusted per Sections 9.2.2 and 9.2.3
- Study medication collected and reviewed for compliance
- Study medication will be dispensed as required
- The next trial visit will be scheduled

## 11. PROCOTOL PROCEDURES

## 11.1. Enrollment

Enrolment should only occur once subject eligibility is confirmed. Each successive subject will be assigned a unique identification number.

# 11.2. Assessment of Efficacy

This is a safety trial and efficacy will not be assessed.

# 11.3. Assessment of Safety

The PI and/or the study staff will monitor the subjects throughout the trial period.

The following safety assessments will be made:

- AEs
- Vital signs (seated blood pressure and pulse)
- Clinical laboratory tests
- 12 lead ECG in triplicate
- Physical examination and neurological evaluation
- C-SSRS

#### 11.3.1. Adverse Events

An AE is any untoward medical occurrence during treatment with a pharmaceutical product in a subject that does not necessarily have a causal relationship with the treatment being administered. An AE can therefore be any unfavorable and unintended sign (including an

Confidential Page 27 of 47

abnormal laboratory finding), symptom, or disease temporally associated with the use of a medicinal (investigational) product, whether or not related to the medicinal (investigational) product.

An untoward medical event occurring prior to the start of study treatment does not meet the above mentioned definition of an AE. Nevertheless, pre-dosing medical history and physical examination anomalies must be documented in the appropriate section of the eCRF. Each subject will be queried for the occurrence of baseline medical anomalies or conditions prior to study drug administration. Included will be an assessment of their grade (mild, moderate, or severe). These events will be reported under medical history or physical examination. During and following a subject's participation in this trial, the investigator must ensure that adequate medical care is provided to a subject for any AE, including clinically significant laboratory values, related to the trial. The subject will be treated and/or followed up until the symptom(s) returns to normal or stabilizes, as judged by the PI. For data management purposes, for subjects completing the study, follow-up information on AE will be terminated at 30 days from the time of onset of the adverse event.

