# 11.4. Methods and Timing for Assessing, Recording, and Analyzing Safety Parameters

# 11.4.1. Eliciting, Documentation and Reporting of Adverse Events, Intercurrent Illnesses, and Subject Diaries

Information on AEs will be derived by questioning the subjects in general and unbiased terms (eg, "How do you feel?" or "How have you been feeling since the last study visit?"), by subjects' spontaneous reports, or by observation. The subject diaries will also be reviewed with the subject for the presence of potential AEs.

AEs will be documented on the source document. The AE will be entered to the AE eCRF pages. The following information will be given for each AE: description of the AE, start date, stop date, severity, action taken, outcome, seriousness, and relationship to the trial medication.

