## 11.4.1.2. Documentation and Reporting of Immediately Reportable Adverse Events

The subject will be examined for any new medical conditions, worsening of the pre-existing ones, or change in the frequency of pre-existing medical condition. Any clinically significant change in pre-existing conditions, new conditions, or change in the frequency of pre-existing conditions post study drug dosing should be entered on the AE page of the eCRF and any medication given in response to the condition should be listed on the concomitant medication page.

All SAEs, whether or not considered attributable to the study drug, must be reported, in the eCRF and on a separate SAE Report Form according to the following procedures. As much information as possible should be supplied at the time of the initial report with at least the following information:

- Name, address, and telephone number of the reporting investigator
- Investigational product(s)
- Protocol number
- Subject identification number, initials, sex and date of birth

Confidential Page 31 of 47

- Description of the AE, reason for serious status, measures taken and outcome (if resolved)
- Likelihood of drug causation of the adverse event assessed by the investigator.

All SAE Reports must be reported to the Clinical Drug Safety Department of the CRO. Copies will be then forwarded to the Sponsor and the Sponsor's Designee for Regulatory Reporting within 24 hours of receipt.

Reports will be addressed to:

The investigator will report all SAEs to the IRB/IEC within 7 working days of the investigator becoming aware of the event. The investigator will inform the IRB/IEC about any SAE occurring during the course of this trial that could adversely affect the safety of the subjects or the performance of the trial.

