2. INTRODUCTION

This Statistical Analysis Plan (SAP) describes the planned statistical analyses to be performed for the analysis of data from Study CLR_11_04, "A Clinical Evaluation of the Safety of When Administered Once Daily to Subjects with Spasticity due to Multiple Sclerosis (MS): An Open Label, Long Term, Safety Trial."

The SAP is prepared to provide a more technical and detailed elaboration of the principal statistical features stated in the protocol. The SAP will ensure that the tables, listings, and figures that will be produced and statistical methods that will be used are complete and accurate and will allow valid conclusions to be drawn. In the development of this SAP, the following documents were used:

- Protocol Number Version 1.0 Amendent 02, 17 Dec 2015
- Electronic Case Report Form (eCRF), 24 Jun 2013

The principles in the following guidance documents are followed in preparation of this SAP:

- International Conference on Harmonisation (ICH) E3 (1995): Structure and Content of Clinical Study Reports
- ICH E6 (1996): Guideline for Good Clinical Practice
- ICH E9 (1998): Statistical Principles for Clinical Trials

In the event that a discrepancy is found between the descriptions in the statistical section of the protocol and this document, the description in this document supersedes the descriptions in the statistical section of the protocol.

The Biostatistician is responsible for updating the SAP throughout the life of the study as needed. The responsible party at SPARC Ltd. will be required to review and approve all versions of the SAP.

Version 1.0

30Oct2017

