6.3 Safety Analysis

6.3.1 Adverse Events

Adverse events recorded from the time the Informed Consent Form is signed until 30 days after the end of the trial will be captured in the trial safety database. For any AE included in this trial's safety database, follow-up information on the AE up to 30 days from the onset of the AE will also be included in the same database. Post-trial AEs not included in this database will be included in a separate pharmacovigilance database, which will be used for generating periodic safety reports.

Treatment-emergent adverse events (TEAEs) will be used for summary and analysis purposes.

All TEAEs will be coded by system organ classification and preferred terms according to version 15.0 of MedDRA®.

When AE start and/or stop dates are missing, the following imputations will be made (subject to medical review):

Missing AE Start Dates

- 1. If onset date is completely missing, then onset date is set to date of first dose
- 2. If year is present and (month and day are missing), or (month is missing but day is present):
 - a. If year = year of first dose, then set date to first dose date
 - b. If year < year of first dose and medication stop month and year are available, then set to first of the end month
 - c. Otherwise if year < year of first dose, then set month and day to December 31st.
 - d. If year > year of first dose, then set month and day to January 1st.
- 3. If month and year are present and day is missing:
 - a. If year=year of first dose and
 - i. If month = month of first dose then set day to day of first dose date
 - ii. If month < month of first dose then set day to last day of month
 - iii. If month > month of first dose then set day to first day of month
 - b. If year < year of first dose then set day to last day of month
 - c. If year > year of first dose then set day to first day of month
- 4. If the AE start date is completely missing and the corresponding stop date is completely missing, the AE start date will remain missing.

Missing AE Stop Dates

If the stop date is completely missing and the event is not ongoing (i.e., an outcome is indicated), the stop day will not be estimated.

If only the day of resolution is unknown, the day will be assumed to the last of the month (e.g. ??-JAN-2011 will be treated as 31-JAN-2011)

If the stop date is completely missing and the event is ongoing, the event will be noted as "Ongoing" in the stop date column in the AE listings.

[figure not shown]

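### A 30-day-from-onset limit on adverse-event follow-up data, read literally, freezes the severity, action taken, outcome and stop date of longer non-serious events, and the SAP does not say whether later data count

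*Protocol*

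**What the plan says.** Protocol 11.3.1 separates care from data. Clinically, the subject is "followed up until the symptom(s) returns to normal or stabilizes, as judged by the PI". For data management purposes, however, "for subjects completing the study, follow-up information on AE will be terminated at 30 days from the time of onset of the adverse event". The clock starts at AE onset, not at the end of the trial, and the sentence covers completers only.

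SAP 6.3.1 captures AEs from consent until 30 days after the end of the trial. It then adds, for any AE in the trial safety database, that "follow-up information on the AE up to 30 days from the onset of the AE will also be included in the same database". This is not limited to completers and does not say what happens to information dated after day 30. The separate pharmacovigilance database (SAP 5.4 and 6.3.1) is described only for post-trial AEs that are not in the trial database.

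Three other places set no 30-day limit:

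- Protocol 11.4.1: "The following information will be given for each AE: description of the AE, start date, stop date, severity, action taken, outcome, seriousness".
- Protocol 9.6.1, for subjects withdrawn because of AEs: "All pertinent information concerning the outcome of such treatment will be entered in the eCRF".
- Protocol 14.2: the eCRF is to hold all data relating to the trial.

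Protocol 11.4.1.4 also continues follow-up of AEs unresolved at trial end until they resolve or their persistence is explained, but it does not say where that information is recorded.

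**The concern.** Long-term safety is the trial's only question, so AEs that last are of particular interest. Taken at its word, Protocol 11.3.1 stops the data record of a completer's AE on day 30 while the site goes on following the patient. A later change in severity, a later action, the final outcome and the stop date would then be known at the site without having to reach the analysis.

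SAP 6.3.1 plans an AE overview by highest severity, action taken and outcome, and a listing with AE duration. Those fields could be incomplete or understated for AEs longer than 30 days. The tables would also pool completers cut at day 30 with subjects withdrawn for AEs, who have no stated cut under Protocol 9.6.1. If SAP 6.3.1 is read as a limit, it contradicts 9.6.1 outright.

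**Working it through.** **1. Does one document settle it?** No. The SAP says that "the description in this document supersedes the descriptions in the statistical section of the protocol". Protocol 9.6.1, 11.3.1 and 11.4.1 lie outside the protocol's statistical section (Section 12), so the clause does not displace them.

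**2. Could a later worsening enter as a further AE?** Perhaps. For the AE form, Protocol 11.4.1.2 says: "Any clinically significant change in pre-existing conditions, new conditions, or change in the frequency of pre-existing conditions post study drug dosing should be entered". That text and the AE definition in Protocol 12.3.3.1 speak of pre-existing conditions, or conditions present before the drug. It is therefore unclear for an AE that began on treatment. A second entry would not supply the first event's outcome or stop date.

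**3. What is captured by another route?**

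- Serious AEs: "All SAEs, whether or not considered attributable to the study drug, must be reported, in the eCRF and on a separate SAE Report Form", with SAE reconciliation between the two databases before clean file (Protocol 14.4).
- Discontinuations: the reason goes on its own eCRF page (Protocol 9.6.1).
- AE incidence by system organ class and preferred term: this needs only the event and its onset.

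What is left is the highest-severity, action-taken and outcome summaries and the listed duration.

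**4. Size.** The plan gives no figure to reproduce and no AE durations. The following is illustration only. Assumptions: exponential duration with median m days (7, 14, 30, 60), onset at day t uniform over a trial of length L, and L = 182 days (26 weeks) or 364 days (1 year). Let k = ln2/m, a = 2^(-30/m) and b = e^(-kL). Losses are measured against capture until 30 days after the subject's end of trial, the cut-off proposed under the fix for an AE starting within the trial.

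- Open at day 30: a.
- Literal reading (data stop at t+30). Share resolving after that but before L+30: a − 2^(-(L−t+30)/m). Averaged over t: a × [1 − (1−b)/(kL)].
- Close-out reading (updates enter during the trial; afterwards only up to 30 days from onset). Share resolving after the later of L and t+30 but before L+30, averaged over t: [(1−a)(a−b)/k + a(30 − (1−a)/k)]/L.

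For example, with m = 30 and L = 182: k = 0.0231, kL = 4.205, a = 0.5, b = 0.0149.

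- Literal: 0.5 × [1 − 0.9851/4.205] = 0.383.
- Close-out: [0.5 × 0.4851/0.0231 + 0.5 × (30 − 0.5/0.0231)]/182 = (10.50 + 4.18)/182 = 0.081.

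| Median duration (days) | Open at day 30 | Literal, L=182 | Literal, L=364 | Close-out, L=182 | Close-out, L=364 |
|---|---|---|---|---|---|
| 7 | 5% | 5% | 5% | 0.8% | 0.4% |
| 14 | 23% | 20% | 21% | 3.7% | 1.9% |
| 30 | 50% | 38% | 44% | 8.1% | 4.1% |
| 60 | 71% | 41% | 54% | 10.0% | 5.7% |

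Numerical averaging gives the same values. For an AE starting on the last trial day (t = L) the loss is 0 on both readings. These shares count missed resolutions. They do not measure missed changes in severity or action taken.

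**The case against.** The strongest reply is that the sentence is a close-out rule and not a cut applied during the trial.

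- It applies to subjects completing the study, and on day 30 of an AE a site cannot know who will complete.
- It follows text about care during and after participation and is tied to data management, which suits a run-out that lets the database close.
- AEs are evaluated at every visit (Protocol Table 1 and Section 10). Protocol 11.4.1 asks for outcome and stop date without limit, and 14.4 has all data entered and source-verified.
- After Week 4 the scheduled gaps are 56, 98 and then about 90 days. A literal cut would often fall before the next visit and bar routine updates learned there.
- The SAP wording is inclusive: such data are also included, and nothing excludes later data.
- The eCRF that the SAP relies on is not among the documents and might show that AE fields stay open.

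Most of this stands. A reader might infer that follow-up after day 30 will certainly be absent from the trial data. The documents do not support that; they leave it open. A reader might also infer that the fatal-event, serious-event or discontinuation tables are biased. They are not shown to be, because those events have their own recording routes; at most their link to the original AE is at risk. Dose changes also have their own listing.

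What remains is that neither document states the close-out meaning. Even under it, an AE open at trial end may go without updates while new AEs are captured for another 30 days.

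**Conclusion.** The point holds as a badly worded data rule that the SAP repeats without resolving. Read literally, it freezes four fields of non-serious AEs lasting beyond 30 days and conflicts in substance with Protocol 11.4.1 and 14.2; if the SAP window is taken as a limit, it conflicts with 9.6.1 as well. On the plausible close-out reading, the loss is limited to updates after trial end. On either reading the effect is confined to a few descriptive AE summaries and one listed variable.

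The true size is unknown. Under the stated assumptions the share of resolutions left out runs from 5% to 54% on the literal reading and from 0.4% to 10% on the close-out reading. These are not estimates for this trial. Confidence is medium, because the intended meaning cannot be settled from the documents. It is worth fixing: long-term safety is the only objective and the remedy is cheap.

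**What to change.** Reword the sentence in Protocol 11.3.1 and the matching one in SAP 6.3.1 so that the data cut-off runs from the end of trial, and check that Protocol 9.6.1 and 11.4.1.4 agree with it:

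> *Updates to any AE in the trial database are recorded and analysed until resolution, or until the later of 30 days after the subject's end of trial and 30 days after AE onset. Later outcomes known for subjects withdrawn for AEs, and fatal outcomes, are included. Events still open are listed as ongoing with the date of last follow-up.*

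Add to SAP 6.3.1 that AE data already entered after day 30 are used. If later data were not collected, report the number and percentage of completers' AEs still open at day 30 beside the outcome summary. If the 30 days was meant only as a run-out for late-onset events, this wording keeps it. Clinical follow-up is unchanged.

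The cost is some extra data entry, site queries for follow-up that was not entered, and cleaning before lock. The protocol edit may need an amendment with sponsor agreement and IRB/IEC approval, unless it counts as purely logistical or administrative (Protocol 14.5). The SAP sentence alone settles the use of data already collected.
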